10.4 Planned analyses

The planned analyses will be detailed in separate statistical analysis plans. There will be two plans, one for the global analyses and one for the analyses of the patients included according to this protocol.

The statistical analyses are planned when the global trial is stopped for either efficacy or futility of the included treatments or when we have reached our recruitment goal of at least 406 patients per arm.

Prior to each statistical analysis, the data in the data base will be exported and the exported data will be locked for further altering of data. A SAP will provide details on the planned statistical analyses. The SAP will be finalized, signed and dated prior to analysis. There will be no efficacy interim analyses according to this protocol.

10.5 Statistical Analysis

10.5.1 Primary analysis

The primary analysis will be identical to the primary analysis according to the WHO core protocol and corresponding statistical analysis plan, restricted to the population included in this add-on trial. The primary analyses assess any effects of treatment allocation on all-cause in-hospital mortality, compared to standard of care, analyzing separately people who already had severe disease at entry (admitted directly to intensive care) and those who did not.

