Patient enrolment and randomization: This will be carried out online via a database created for this purpose by the WHO. Adults (age \geq 18 years) recently hospitalized, or already in hospital, with definite COVID and, in the view of the responsible doctor, no contra-indication to any of the study drugs will be randomly allocated between

- Local SoC alone,
OR local SoC plus
- Remdesivir

Data reported before randomization via the WHO database:

- Hospital and randomizing doctor
- Confirmation that informed consent has been obtained
- Patient identifiers, age and sex
- Patient characteristics (yes/no): current smoking, diabetes, heart disease, chronic lung disease, chronic liver disease, asthma, HIV infection, active tuberculosis.
- COVID-19 severity at entry (yes/no): shortness of breath, being given oxygen, already on a ventilator, and, if lungs imaged, major bilateral abnormality (infiltrations/patchy shadowing)
- Whether the study drug is currently NOT AVAILABLE at the hospital.

Inclusion criteria

1. Adult patients, 18 years and older
2. Confirmed SARS-CoV-2 infection by PCR
3. Admitted to the hospital ward or the ICU
4. Subjects (or legally authorized representative) provide informed consent prior to initiation of the study
5. No anticipated transfer within 72 hours to a non-study hospital

Exclusion criteria

1. Severe co-morbidity with life expectancy $<$ 3 months according to investigators assessment
2. ASAT/ALAT $>$ 5 times the upper limit of normal
3. Acute co-morbidity within 7 days before inclusion such as myocardial infarction
4. Known intolerance to the study drug
5. Pregnancy or breast feeding
6. Any reason why, in the opinion of the investigators, the patient should not participate

7. Participation in a potentially confounding drug or device trial during the course of the study
8. Already receiving any of the current study drug(s)
9. Patients on concomitant medications, which is part of the list of prohibited medications have to be excluded from the current study.

Prohibited medication:

Haloperidol, carbamazepine, phenytoin, rifampin, phenobarbital, isoniazid, pyrazinamide, nevirapine, ritonavir, sodium valproate/valproic acid

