2.3 Study design

The NOR-SOLIDARITY study is an adaptive, randomized, open clinical multicentre trial to evaluate the safety and efficacy of possible therapeutic agents in hospitalized adult patients diagnosed with COVID-19. See the WHO COVID-19 core protocol (Appendix 1) for the core trial design. This multicentre add-on trial will follow the WHO core protocol version 10 dated 22.03.2020 but will add additional secondary and exploratory endpoints.

Adults (age ≥ 18 years) recently hospitalized, or already in hospital, with definite COVID and, in the view of the responsible doctor, no contra-indication to any of the study drugs will be randomly allocated between

- Local standard of care alone,
OR local standard of care plus
- Remdesivir (one intravenous loading dose, then daily infusions for altogether 10 days)

The primary objective of the trial is to investigate the effect of Remdesivir on all-cause in-hospital mortality compared to standard of care.

Patients will be followed daily during hospitalization, after 28 days by telephone/sms and then by an outpatient clinical visit after 3 months.

In the core protocol follow-up data are only collected at discharge. In this protocol subjects will additionally be assessed for efficacy and safety both during hospitalization and after hospitalization.

In addition to the global independent data and safety monitoring board (DSMB) as described in the core protocol, a national DSMB will monitor the safety and risk-benefit of the trial interventions in the Norwegian population.

[figure not shown]

Figure 2: The Investigational NOR-SOLIDARITY protocol

3 Objectives and endpoints

Objectives	Endpoints (Outcome measures)
Primary (in line with WHO core protocol)	
To investigate the effect of Remdesivir on all-cause in-hospital mortality compared to standard care.	All-cause in-hospital mortality
Secondary (in line with WHO core protocol)	
Assess the effect of Remdesivir on hospital duration, receipt of ventilation or intensive care, and to identify any serious adverse reactions.	During hospitalization 
 • Receipt of mechanical ventilation • Time to first receiving and duration of mechanical ventilation • Receipt of intensive care • Duration of intensive care • Occurrence of Suspected Unexpected Serious Adverse Reactions (SUSARs)
Secondary (as addition to the WHO core protocol)	

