4.1 Inclusion criteria (as described in WHO COVID 19 core protocol)

1. Adult patients, 18 years and above
2. Confirmed SARS-CoV-2 infection by PCR
3. Admitted to the hospital ward or the ICU
4. Subjects (or legally authorized representative) provide informed consent prior to initiation of the study
5. No anticipated transfer within 72 hours to a non-study hospital

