4.4 Baseline characteristics

According to the CRF a description of the included patients co-morbidity, ongoing treatment and performance status (Frailty score) will be required. Severe disease is defined as patients which need ICU management and mild/moderate disease is defined as people which can be treated at the hospital ward.

A pregnancy test will be performed in all women of childbearing potential. For the purpose of this document, a woman is considered of childbearing potential (WOCBP), i.e. fertile, following menarche and until becoming post-menopausal unless permanently sterile. Permanent sterilization methods include hysterectomy, bilateral salpingectomy and bilateral oophorectomy

5 Study products and study drug regimes

See core protocol (Appendix 1 and SOP-4 to SOP-7b). Note that this protocol currently only includes Remdesivir as study drug.

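### Section 10.5.1 defines severe disease at entry by route of admission, which conflicts with section 4.4 and places ward-to-ICU transfers in the non-severe group

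*Protocol*

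**What the plan says.** Protocol section 10.5.1 makes all-cause in-hospital mortality the primary analysis and reports it by severity, "analyzing separately people who already had severe disease at entry (admitted directly to intensive care) and those who did not". The same section states that "The primary analysis will be identical to the primary analysis according to the WHO core protocol"; the core protocol is a separate appendix and is not reproduced here.

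Section 4.4 gives its own definition: "Severe disease is defined as patients which need ICU management", while "mild/moderate disease is defined as people which can be treated at the hospital ward". It does not mention how the patient reached the ICU.

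Eligibility sets no condition on route or on time since admission. Section 2.3 covers adults "recently hospitalized, or already in hospital, with definite COVID", and inclusion criterion 3 in section 4.1 reads "Admitted to the hospital ward or the ICU".

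The synopsis lists the severity items entered in the WHO database before randomisation: "COVID-19 severity at entry (yes/no): shortness of breath, being given oxygen, already on a ventilator", plus lung imaging where done. Neither ICU location nor admission route is on that list.

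**The concern.** Admission to hospital and entry to the trial are different moments, and the protocol allows time between them. Section 10.5.1 names a state at trial entry and then defines it by an event at hospital admission. For patients who change level of care in between, the two disagree.

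What is at stake is what each half of the primary result means. Section 2.1.1 asks whether early treatment is needed for benefit, and section 7.4.1 anticipates particular benefit in ICU patients. A split by severity bears on both. If patients in ICU at randomisation sit in the group labelled non-severe, that group's mortality and treatment effect are a mixture, and the severe group holds only part of the ICU population. Two written definitions of severe disease also leave it open which one governs the primary analysis.

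**Working it through.** **Comparing the definitions.** Each eligible patient type is classified under both sections, reading 10.5.1 literally.

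| Patient at randomisation | Section 4.4 | Section 10.5.1 |
|---|---|---|
| Admitted to ward, still on ward | Mild/moderate | Non-severe |
| Admitted directly to ICU, still in ICU | Severe | Severe |
| Admitted to ward, since moved to ICU | Severe | Non-severe |
| Admitted directly to ICU, since stepped down to ward | Mild/moderate | Severe |

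The last two rows are eligible under sections 2.3 and 4.1, and the sections disagree on both. This result needs no numerical assumption.

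**The plan's own figures.** Section 10.1 gives an ICU share of 70/268 = 26.1%, stated as 26%. The target of 406 per group (26% v 16%, 2.5% two-sided, 90% power) reproduces exactly with the unpooled normal approximation: (2.2414 + 1.2816)² × (0.26×0.74 + 0.16×0.84)/0.10² = 405.6, rounded up to 406. No stated number is wrong, and none depends on the severity definition.

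**Illustration of size.** Inputs:
- Share in ICU at randomisation: 26%. This is an assumption borrowed from section 10.1, where the figure is a national snapshot of hospitalised patients.
- Overall mortality: 5%, the standard-of-care figure in section 10.1.
- q, the fraction of those ICU patients who came via the ward: assumed 10%, 25%, 50% or 75%.
- m, mortality among patients in ICU at randomisation: assumed 10% or 15%.
- Stepped-down patients are ignored, because the protocol gives nothing to size them with.

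Per 100 patients, 74 are on the ward and 26 are in ICU. Ward deaths are W = 5 − 26m, which is 2.4 for m = 10% (ward mortality 2.4/74 = 3.24%) and 1.1 for m = 15% (1.1/74 = 1.49%).

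- Share of the non-severe group that is in ICU: 26q/(74 + 26q)
- Share of that group's deaths: 26qm/(26qm + W)
- Mortality of that group: (26qm + W)/(74 + 26q)

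| q | ICU share of non-severe group | Share of its deaths, m = 10% | Share of its deaths, m = 15% | Group mortality, m = 10% | Group mortality, m = 15% |
|---|---|---|---|---|---|
| 10% | 3.4% | 9.8% | 26.2% | 3.47% | 1.95% |
| 25% | 8.1% | 21.3% | 47.0% | 3.79% | 2.58% |
| 50% | 14.9% | 35.1% | 63.9% | 4.25% | 3.51% |
| 75% | 20.9% | 44.8% | 72.7% | 4.65% | 4.30% |

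For example, with q = 50% and m = 15%, ICU deaths are 26 × 0.5 × 0.15 = 1.95, and 1.95/(1.95 + 1.1) = 63.9%. Rounding ward mortality to 1.5% lowers the top value from 72.7% to 72.5%.

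At the two-arm goal of 812 patients, 26% is about 211 in ICU. Of these, about 21, 53, 106 or 158 would be counted as non-severe at the four values of q.

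**The case against.** The strongest reply is that the parenthesis is only a gloss. The operative words concern severe disease already present at entry, section 4.4 says what severe disease is, and the synopsis uses entry for the time of randomisation. On that reading, a patient ventilated in ICU at randomisation is severe whatever the route. This is plausible and may be what was meant. But the parenthesis is the only definition given where the analysis is specified, and no sentence says that section 4.4 overrides it.

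Second, section 10.5.1 claims identity with the WHO core analysis, and a national SAP is to follow; either may settle the rule. That does not remove the conflict within this protocol. It does mean that any new wording must be checked against the core definition.

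Third, the protocol expects too few patients for mortality and relies on the global analysis. At 812 patients and 5% mortality, about 41 deaths (812 × 0.05 = 40.6) are expected, so either split will be imprecise. This stands and limits the practical weight of the point.

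Four stronger inferences are tempting but unsupported:
- **A biased treatment effect.** Admission route and ICU status at entry both precede randomisation, so the comparison within each group stays valid.
- **Non-severe deaths would be mostly ICU deaths.** That holds only in part of the assumed range; at the lower end the share is about 10%.
- **This is the only analysis addressing severity.** That cannot be said without the SAP, and section 10.5.2 leaves its list of methods open.
- **A new data item is needed.** The synopsis list covers the WHO database only. Section 7.2 provides a separate national eCRF, section 7.1 collects daily clinical data from inclusion, and receipt and duration of intensive care are endpoints, so ICU status may already be recorded.

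**Conclusion.** The point holds as a contradiction in the definition that splits the primary analysis. As written, section 10.5.1 puts ward-to-ICU transfers in the non-severe group and stepped-down direct admissions in the severe group, contrary to section 4.4. The harm is to interpretation: high-risk ICU patients are mixed into a group labelled non-severe.

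The number affected cannot be obtained from the protocol. The illustrative ranges, about 3–21% of the non-severe group and about 10–73% of its deaths, rest on the borrowed 26% and on assumed values for the via-ward fraction and ICU mortality. They show that the effect could be small or large, and they are not estimates for this trial. The contradiction does not depend on them. It should be fixed, but it does not invalidate the primary comparison.

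**What to change.** In section 10.5.1, replace the parenthesis with status at randomisation, for example in ICU or on a ventilator at randomisation, and use the same definition in section 4.4. Check the wording against the WHO core definition. If the two differ, either adopt the core definition throughout or say that this split departs from the core analysis.

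Confirm that ICU status at randomisation can be taken from the national eCRF, and add a yes/no item only if it cannot.

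The cost is one sentence in each of two sections and, at most, one eCRF field. Sample size, procedures and patient care do not change. Make the change before database lock, so that the choice between two written definitions is not left until allocation is known.

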10.5.2 Secondary analyses

Between group comparisons will be performed for the primary variable on the per-protocol population in addition to secondary efficacy endpoints on both efficacy populations (ITT and PP populations).

The between-group comparisons for secondary variables will be tested as for the primary variable where applicable and additional analyses will be performed based on the following methods (but not limited to):

- Continuous secondary variables will be subject to repeated measures mixed models or appropriate non-parametric alternatives
- Binary response variables will be analysed using logistic regression (possibly adjusting for within-subject dependencies by generalized estimating equations or mixed models) or chi-square/Mantel-Haenszel tests
- Time-to-event variables will be analysed using the Kaplan-Meier method and comparisons between the two groups will be performed using the log rank test, Cox regression analyses or appropriate parametric models such as the gamma or Weibull model.

Unless otherwise specified, all statistical hypotheses will be tested as the primary variable, i.e. with an assessment of superiority of the estimated difference between the groups. All efficacy analyses will be presented with the results from the hypothesis testing (by p-value) in addition to estimates and 95% confidence limits of the treatment effect.

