10.1 Determination of Sample Size

Recruitment will continue until the global core trial is concluded (Appendix 1). Assuming 5% all-cause in-hospital mortality in the standard of care arm and that 2% absolute risk difference is regarded a clinically meaningful difference, 2377 patients in each arm are required to conclude with benefit on a 2.5% two-sided significance level with 90% power. This calculation adjusts for multiple testing using Bonferroni correction. If even more proof is needed, 3412 patients in each arm are needed to conclude with benefit on a 1% two-sided significance level with 95% power. We will not be able to reach these numbers in this trial alone but will rely on the combined analyses of all participating trials in the global consortium.

In this trial we will therefore aim to show a difference in receipt of intensive care. Currently in Norway there are 70 patients in intensive care out of 268 (26%). With a minimum clinically important difference of 10% our goal is to randomize 406 patients in each group to be 90% certain to conclude with benefit on the 2.5% two-sided level.

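### Kaplan-Meier for time to mechanical ventilation would overstate the in-hospital risk, mainly through live discharge, and ventilation and ICU durations are shortened by death with no rule for it

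*Protocol*

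**What the plan says.** The table in Protocol section 3 lists, among the secondary endpoints measured during hospitalization, "Time to first receiving and duration of mechanical ventilation" and "Duration of intensive care". "Receipt of mechanical ventilation" and receipt of intensive care are separate binary endpoints. The synopsis counts time to ventilation among the major secondary outcomes.

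Section 10.5.2 assigns methods by type of variable. For times to event: "Time-to-event variables will be analysed using the Kaplan-Meier method and comparisons between the two groups" are to use the log-rank test, Cox regression or a parametric model. For continuous variables, the class into which durations would fall: "Continuous secondary variables will be subject to repeated measures mixed models or appropriate non-parametric alternatives". The list is open: "additional analyses will be performed based on the following methods (but not limited to"). The same section promises an estimate and 95% confidence limits for every efficacy analysis, as well as a p-value.

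Section 7.1 collects daily clinical data until discharge or death. Section 2.3 adds a telephone or text contact at 28 days, and section 3 lists overall survival at that time. No section says how death or live discharge enters the time-to-ventilation analysis, or how death is scored when it ends a ventilation episode or an ICU stay. Section 10.4 leaves the details to a SAP, which is not at hand.

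**The concern.** Two separate problems arise if the text is followed as written.

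**Time to ventilation.** A patient who goes home, or who dies unventilated, can no longer be ventilated in hospital. Daily follow-up ends at exactly those two events, so with Kaplan-Meier and no competing event named, censoring at both is the natural reading. Kaplan-Meier then treats these patients as if they still faced the risk of those left in hospital. The curve describes a hypothetical setting in which nobody dies or is discharged, not the risk that patients face. The absolute risks by arm, and any risk difference read from the curves, would be wrong.

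**Durations.** Death ends ventilation and ICU stay. An unadjusted duration therefore scores an early death as a short and apparently favourable stay. If durations are compared only among patients who received the support, the comparison is also between groups formed after randomisation. Mixed models and non-parametric tests do not by themselves deal with either point.

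**Working it through.** **The plan's own figure.** Section 10.1 sizes the trial on receipt of intensive care: 26% (70/268) against 16%, 2.5% two-sided, 90% power. With unpooled variance, n = (0.26×0.74 + 0.16×0.84) × (2.2414 + 1.2816)² / 0.10² = 0.3268 × 12.411 / 0.01 = 405.6, so 406 per group, as stated. It rests on a binary endpoint and nothing below touches it.

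**Inputs for time to ventilation.** The protocol gives no rates of ventilation, unventilated death or discharge, so all three are assumed. Take constant daily hazards of v = 0.02 (ventilation), d = 0.005 (death without ventilation) and s = 0.075 (live discharge), total 0.10, over 28 days.

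- True risk (cumulative incidence): v/0.10 × (1 − e^(−0.10×28)) = 0.2 × (1 − e^(−2.8)) = 18.8%.
- One minus Kaplan-Meier, death and discharge censored: 1 − e^(−0.02×28) = 1 − e^(−0.56) = 42.9%.
- One minus Kaplan-Meier, deaths censored but discharged patients kept event-free: the risk set is 0.75 + 0.25e^(−0.10t), which gives 1 − exp[−0.8 × ln(1/(0.75 + 0.25e^(−2.8)))] = 19.3%.

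The excess is 42.9 − 18.8 = 24.1 points, of which censoring deaths alone accounts for 19.3 − 18.8 = 0.5. Discharge produces the rest.

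**Sensitivity to mortality.** These hazards imply 0.005/0.10 × (1 − e^(−2.8)) = 4.7% dying unventilated, almost all of the 5% total in-hospital mortality in section 10.1. With d = 0.001, unventilated deaths are about 1% and the true risk is 0.02/0.096 × (1 − e^(−2.688)) = 19.4%. With d = 0.002, they are about 2% and the true risk is 19.3%. One minus Kaplan-Meier stays at 42.9%, so the error does not depend on high mortality.

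**Range with discharge and death censored.** Fix the 28-day proportions and write T for their sum. Then one minus Kaplan-Meier = 1 − (1 − T)^(p/T), with p the true risk of ventilation. With 2% dead unventilated (assumed):

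| True risk | Discharged by day 28 | One minus Kaplan-Meier |
|---|---|---|
| 10% | 60% | 16.2% |
| 10% | 70% | 18.9% |
| 15% | 60% | 24.9% |
| 15% | 70% | 29.7% |

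**Death alone, discharged patients kept at risk.** Even if all 5% of deaths were unventilated and 26% were ventilated (the ICU rate borrowed as a high value), one minus Kaplan-Meier is 1 − 0.69^(0.26/0.31) = 26.7%, an excess of 0.7 points.

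**Effect of extra deaths on the comparison.** In that last setting, double the death hazard in one arm and leave the ventilation hazard alone. One minus Kaplan-Meier is 26.7% in both arms, while the cumulative incidence of ventilation falls from 26.0% to 25.3%.

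**Durations.** Assume that ventilated survivors need 14 days and ventilated patients who die do so after 6 days. At 20% mortality among the ventilated, the mean is 0.8×14 + 0.2×6 = 12.4 days. At 40% it is 0.6×14 + 0.4×6 = 10.8 days. Doubling mortality shortens the mean by 1.6 days.

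**The case against.** The strongest reply is that the protocol is silent rather than wrong. It does not say that deaths or discharges are censored, it does not commit to unadjusted durations, its list of methods is open, and censoring rules are ordinary SAP content. That stands in part. But an open list adds methods and does not withdraw the one it names, and Kaplan-Meier on data that stop at discharge or death leads to censoring by default.

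A reader might infer more: that log-rank is invalid here, or that extra early deaths make a drug look better on time to ventilation. The documents do not support that. With deaths and discharges censored, log-rank and Cox compare the cause-specific hazard of ventilation, and that comparison is valid. In the calculation above, extra deaths left Kaplan-Meier unchanged and lowered the cumulative incidence. Extra deaths lower one minus Kaplan-Meier only when censoring is informative, for example if the patients likeliest to die are also those likeliest to need ventilation.

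A reader might also extend the point to receipt of intensive care, because a ward death without ICU counts there as no ICU. That endpoint is binary, so Kaplan-Meier does not apply to it. Replacing it with a composite of ICU or death is a design preference, not the correction of an error.

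Finally, safeguards exist. In-hospital mortality is primary, 28-day survival is reported, and section 10.5.3 analyses death through three months alone and in a safety composite. A harmful drug would not pass unnoticed. These safeguards do not correct the ventilation risk or the durations themselves.

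**Conclusion.** The point holds for secondary endpoints only.

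- **Time to ventilation.** If discharge and death are censored, the reported risk is too high: 42.9% against 18.8% under the assumed hazards, and 16.2% to 29.7% against true risks of 10% to 15% in the other scenarios. Nearly all of this comes from live discharge. Death alone adds less than one point at the protocol's 5% mortality. The size rests on assumed constant hazards. The direction does not depend on the particular values.
- **Durations.** Higher mortality can look like benefit, by 1.6 days in the assumed example. This depends on deaths occurring earlier than the end of support in survivors, and on durations being compared without a rule for death.

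The arm comparison by log-rank or Cox is not undermined. The primary endpoint, the binary ICU endpoint and the sample size are unaffected.

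**What to change.** **Time to ventilation.** Replace Kaplan-Meier with the Aalen-Johansen cumulative incidence to day 28, with death as a competing event and patients discharged alive kept event-free to day 28. Keep log-rank or Cox, described as a comparison of the rate of ventilation among patients still alive, in hospital and not yet ventilated. Show the cumulative incidence of death without ventilation beside it by arm, because the cumulative incidence of ventilation on its own also falls when deaths rise.

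**Durations.** Analyse ventilator-free and ICU-free days to day 28 in all randomised patients, with death ranked worst and a rank-based test. Report the durations themselves descriptively, by survival status.

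**Cost.** Wording in section 10.5.2 and the SAP. Daily in-hospital data and 28-day survival are already collected, and the sample size does not change. There are two drawbacks. Ventilator-free and ICU-free days mix death with resource use. Ventilation or intensive care after discharge is assumed absent unless the day-28 contact asks about it, so a question on readmission there would help.
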